1.1 Synopsis

Protocol Title: A Phase 1, Randomized, Placebo-controlled, Double-blind, Multiple Ascending Dose Study to Investigate Safety, Tolerability, and Pharmacokinetics of Oral Doses of TCK-276 in Patients with Rheumatoid Arthritis

Brief Title: A Study to Investigate Safety, Tolerability, and Pharmacokinetics of Oral Doses of TCK-276 in Patients with Rheumatoid Arthritis

Sponsor Protocol No.: TCK-276-102

Study Phase: 1

Sponsor: Teijin America, Inc.

Rationale:

Rheumatoid arthritis (RA) is an autoimmune disease characterized by synovial inflammation and hyperplasia. Activated lymphocytes and macrophages produce various proinflammatory mediators which recruit synovial fibroblasts to the joint and activate them. Proliferation of activated synovial fibroblasts further increases production of proinflammatory mediators and tissue-degrading proteinase such as matrix metalloproteinase-3 (MMP-3), resulting in irreversible destruction of bone and cartilage. The current treatment approaches include conventional, biological, and targeted synthetic disease modifying antirheumatic drugs (DMARDs). However, a high proportion of patients only show a partial response or fail to respond to DMARDs currently on the market even used in combination. Therefore, there is a persistent unmet medical need for novel orally active agents with greater efficacy and equivalent or better safety with an alternative mechanism of action.

Teijin America, Inc., (hereafter referred to as Sponsor) has developed TCK-276 (Laboratory code number: TEI-T01276) as a novel synthetic DMARD with an alternative mechanism of action for the treatment of RA. The Sponsor has conducted the Phase 1 single ascending dose (SAD) study using an orally administered capsule containing 5 mg or 50 mg of TCK-276. The Sponsor thereafter plans to develop TCK-276 using an orally administered tablet containing 10 mg or 25 mg of TCK-276.

TCK-276 is a highly potent, orally active, and selective cyclin dependent kinase 4/6 (CDK4/6) inhibitor. Historically, CDK4/6 has been extensively explored as a target for anti-cancer therapeutics, however there is also mechanistic evidence to suggest that CDK4/6 contributes to

the pathogenesis of RA. Cyclin dependent kinase 4/6 is a key regulator at G1/S phase checkpoint in the cell cycle. Cyclin dependent kinase 4/6 forms a complex with D-type cyclins (CycD) and phosphorylates retinoblastoma protein (Rb), leading to depression of transcription factor E2F to accelerate S phase transition. Thus, inhibition of CDK4/6 leads to G1 arrest, and cell cycle progression is attenuated in synovial fibroblasts. In addition to the regulation of cell cycle, CDK4/6 has been reported to mediate the production of MMP-3 and monocyte chemoattractant protein 1 via Rb-independent and dependent pathways. Cyclin dependent kinase 4/6 likely contributes to the pathogenesis of RA by mediating the proliferation of synovial fibroblasts and the production of MMP-3. The inhibition of CDK4/6 may serve a useful therapeutic strategy for RA patients, particularly those with an inadequate response to existing DMARDs.

Objectives and Endpoints:

Objectives	Endpoints

Primary
 
• To evaluate the safety and tolerability of multiple oral doses of TCK 276 in patients with rheumatoid arthritis (RA)	
• Safety and tolerability endpoints: The following safety and tolerability variables will be recorded at regular intervals during the study:
○ Vital signs measurements: supine blood pressure, pulse, body temperature, and respiratory rate○ Cardiac safety for arrhythmias, abnormalities including PR interval, QRS interval, RR interval, QT interval, and QT interval corrected for heart rate (QTc) (Fridericia's correction [QTcF]) as assessed by 12-lead electrocardiogram (ECG) and cardiac telemetry○ Incidence of laboratory abnormalities: hematology, clinical chemistry, coagulation, and urinalysis○ Incidence and severity of adverse event (AE) and adverse event of special interest (AESI) (i.e., gastrointestinal toxicity and pulmonary symptoms indicative of interstitial lung disease) assessments○ Physical examinations

Objectives	Endpoints

Secondary
 
• To evaluate pharmacokinetic (PK) of TCK-276 and its metabolite (TEI-W00595) in patients with RA after multiple ascending dose (MAD) administration	
• PK endpoints 
The following PK parameters for TCK-276 and TEI-W00595 will be determined, if calculable:
 
○ C_{max}: Maximum plasma concentration determined directly from the concentration-time profile (Days 1 and 7)○ t_{max}: Time of maximum plasma concentration determined directly from the concentration-time profile (Days 1 and 7)○ AUC_{tau}: Area under the plasma concentration-time curve over a dosing interval, $\tau = 24$ hours (Days 1 and 7)○ AUC_{0-t}: Area under the plasma concentration-time curve up to last measurable concentration (Days 1 and 7)○ AUC_{0-inf}: Area under the plasma concentration-time curve from pre-dose (time 0) extrapolated to infinite time (Days 1 and 7)○ MRT_{last}: Mean residence time up to last measurable concentration (Day 1 only)○ MRT_{0-inf}: Mean residence time extrapolated to infinity (Days 1 and 7)○ $t_{1/2}$: Terminal elimination half-life (Days 1 and 7)○ CL/F: Apparent total body clearance (Days 1 and 7), determined for parent only○ V_z/F: Apparent volume of distribution based on terminal phase (Days 1 and 7), determined for parent only○ Metabolic ratio (MR) for C_{max}: Molar metabolic ratio of C_{max} calculated as $(C_{max} [\text{metabolite}] \times \text{molecular weight of parent}) / (C_{max} [\text{parent}] \times \text{molecular weight of metabolite})$ (Days 1 and 7)

Objectives	Endpoints
	
○ MR for area under the plasma concentration-time curve (AUC): Molar metabolic ratio of AUC calculated as $(AUC_{\text{metabolite}}) \times \text{molecular weight of parent} / (AUC_{\text{parent}}) \times \text{molecular weight of metabolite}$ (Days 1 and 7)○ C_{trough}: Concentration in a dosing period defined as the pre-dose concentration of the day○ $R_{\text{acc}} (C_{\text{max}})$: Accumulation ratio based on C_{max}: Calculated as C_{max} on Day 7/C_{max} on Day 1○ $R_{\text{acc}} (AUC_{\text{tau}})$: Accumulation ratio based on AUC_{tau}: Calculated as AUC_{tau} on Day 7/AUC_{tau} on Day 1 
The following urinary PK parameters for TCK-276 will be determined in this study:
 
○ A_e: Amount of study drug excreted unchanged in the urine (Days 1 and 7)○ F_e: Percentage of study drug excreted unchanged in the urine (Days 1 and 7)○ CL_r: Renal clearance (Days 1 and 7) 
Other PK parameters will be determined if needed.

Exploratory 
● To evaluate the effect of TCK-276 on disease activity and biomarkers in patients with RA	
● Exploratory endpoints 
The following exploratory disease activity parameters for RA will be assessed:
 
○ American College of Rheumatology (ACR) 20/50/70 response criteria○ Disease activity score 28 (DAS28)○ Clinical disease activity index (CDAI)○ Simplified disease activity index (SDAI) 
The following exploratory biomarkers will be assessed:
 
○ Matrix metalloproteinase-3 (MMP-3)○ Granulocyte macrophage colony-stimulating factor (GM-CSF)

Objectives	Endpoints
	
○ C-X-C motif chemokine ligand 10 (CXCL10)○ C-C motif chemokine ligand 2 (CCL2)○ Cartilage oligomeric matrix protein (COMP)○ Tumor necrosis factor (TNF)-alpha○ TNF-R1○ Interleukin-6 (IL-6)

Overall Design:

This is a Phase 1, multi-center, double-blind, randomized, placebo-controlled, multiple ascending dose (MAD) study to evaluate the safety, tolerability, and pharmacokinetics (PK) of orally administered TCK-276 in both males and females with RA. Blood samples for possible future pharmacogenetic, possible future metabolite assessments, and possible future pharmacodynamic (PD) assessments will be collected.

A total of thirty-two (32) patients with RA will be enrolled in this clinical study. This MAD study will consist of 4 cohorts of 8 patients (6 active treatment and 2 matching placebo, or a 3:1 ratio), each receiving an oral dose of TCK-276 or matching placebo for 7 days (once daily [QD] under fed condition). The first cohort will be divided into 2 subgroups to implement the sentinel dosing approach. Within the cohort, the first subgroup will consist of 2 sentinel patients; one patient will receive TCK-276, and one patient will receive matching placebo. The second subgroup will consist of 6 patients (5 active treatment, 1 matching placebo). Individual patients in the second subgroup will be dosed at least 72 hours after the first dose of the second sentinel patient of the first subgroup following a decision by the Investigators based on all available safety data from the sentinel patients up to 48 hours post-dose. Subsequent cohorts (cohort 2-4) will not include the sentinel dosing approach.

Patients will be admitted to the site from the morning of Day -1 and sequestered for the duration of the treatment (dosing) period. Each patient will receive QD oral doses of either TCK-276 or matching placebo administered as tablets under fed condition in the morning of Day 1 to Day 7. The patients will be discharged on Day 10. The planned dose levels to be tested are 10 mg (Cohort 1), 25 mg (Cohort 2), 75 mg (Cohort 3), and 150 mg (Cohort 4) of TCK-276. Based on the results from the SAD study (5 mg to 185 mg dosing) and the projected clinical effective dose (i.e., 75 mg), 10 mg is selected as the starting dose level in the MAD study. The dose in Cohorts 2, 3, and 4 may be adjusted based on the safety and PK results from the previous cohorts, if necessary. The overall exposure to TCK-276 (in terms of geometric mean area under

the plasma concentration-time curve over a dosing interval [AUC_{tau}, tau = 24 hours] on Day 7 would not be expected to exceed [REDACTED]
[REDACTED].

Dose escalation will only be allowed after blinded assessment of all safety, tolerability, and PK data up to Day 10 from each previous cohort evaluated by Investigators, Medical Monitor, and Sponsor representatives during the Safety Review Committee (SRC) meeting.

Brief Summary:

The purpose of this study is to evaluate the safety, tolerability, and PK of multiple orally administered TCK-276 in both males and females with RA.

Study details include:

- Study duration: approximately 42 days
- Treatment duration: Up to 11 days (Day -1 to Day 10)
- Visit frequency: Screening Visit, Days -1 to 10 Visits; Follow-up/end of treatment (EOT) Visit. Following discontinuation of TCK-276, patients will be followed unless they withdraw their informed consent for study participation.

Number of Patients:

A total of 32 patients with RA are planned for enrollment and randomized into 4 cohorts with 8 patients per cohort. Within each cohort, 6 patients will be randomized to TCK-276 and 2 patients will be randomized to matching placebo.

Note: “Enrolled” means a participant’s, or their legally acceptable representative’s, agreement to participate in a clinical study following completion of the informed consent process and Screening. Potential participants who are screened for the purpose of determining eligibility for the study, but do not participate in the study, are not considered enrolled, unless otherwise specified by the protocol. A participant will be considered enrolled if the informed consent is not withdrawn prior to participating in any study activity after Screening.

Intervention Groups and Duration:

This MAD study will consist of 4 cohorts of 8 patients (6 active treatment and 2 matching placebo, or a 3:1 ratio), each receiving an oral dose of TCK-276 or matching placebo for 7 days (QD under fed condition). The first cohort will be divided into 2 subgroups to implement the sentinel dosing approach. Within the cohort, the first subgroup will consist of 2 sentinel patients;

one patient will receive TCK-276, and one patient will receive matching placebo. The second subgroup will consist of 6 patients (5 active treatment, 1 matching placebo). Individual patients in the second subgroup will be dosed at least 72 hours after the first dose of the second sentinel patient of the first subgroup following a decision by the Investigators based on all available safety data from the sentinel patients up to 48 hours post-dose. Subsequent cohorts (cohort 2-4) will not include the sentinel dosing approach.

Patients will be admitted to the site from the morning of Day -1 and sequestered for the duration of the treatment (dosing) period. Each patient will receive QD oral doses of either TCK-276 or matching placebo administered as tablets under fed condition in the morning of Day 1 to Day 7. The patients will be discharged on Day 10. The planned dose levels to be tested are 10 mg (Cohort 1), 25 mg (Cohort 2), 75 mg (Cohort 3), and 150 mg (Cohort 4) of TCK-276. Based on the results from the SAD study (5 mg to 185 mg doses) and the projected clinical effective dose (i.e., 75 mg), 10 mg is selected as the starting dose level in the MAD study. The dose in Cohorts 2, 3, and 4 may be adjusted based on the safety and PK results from the previous cohorts, if necessary.

Dose Group	Treatment Assignment	
1	10 mg TCK-276 (N = 6)	Placebo (N = 2)
2	25 mg TCK-276 (N = 6)	Placebo (N = 2)
3	75 mg TCK-276 (N = 6)	Placebo (N = 2)
4	150 mg TCK-276 (N = 6)	Placebo (N = 2)

[figure not shown]
Data Monitoring/Other Committee:

A SRC will be appointed for this study. The SRC meeting will take place to review safety and PK data during each dose level. The SRC will evaluate the safety and tolerability data up to Follow-up/EOT Visit and available PK data up to Day 10 to determine the next dose for the subsequent cohort.

1.2 Schema

Figure 1–1 **Study Design**

Each Cohort: active (N=6); placebo (N=2)
Dose in Cohorts 2, 3, and 4 may be adjusted based on the safety and PK results from the previous cohorts, if necessary. The SRC will evaluate the safety, tolerability and available PK data to determine the next dose for the subsequent cohort.

N = number of patients; PK = pharmacokinetics; SRC = Safety Review Committee.

1.3 Schedule of Activities

Table 1-1 Schedule of Activities

Evaluation	Screening visit	Treatment period					Follow-up/ End of treatment	Early termination procedures
		Days						
		-28 to -2	-1	1	2-7	8, 9	10	14
Informed consent	X							
Admission		X						
In-house stay		X	X	X	X	X	X	
Ambulatory visits	X						X	X
Discharge							X	
Inclusion/exclusion criteria	X	X	X					
Medical history	X	X						
Disease activity data (ACR20/50/70, DAS28, CDAI, SDAI)			X ¹	X ²				
Blood sampling for ESR, assessed as part of disease activity data			X ¹	X ²				
Demographics	X							
Weight and height (height only at Screening)	X	X					X	
Viral serology (HBsAG, anti-HBc, anti-HCV, anti-HIV)	X							
Drug, alcohol, and cotinine screen	X	X						
SARS-CoV-2 real time RT-PCR	X	X						
IGRA-TB test (Quantiferon)	X							
Chest X-ray	X							
Randomization			X					
Study drug administration			X	X				

Evaluation	Screening visit	Treatment period					Follow-up/ End of treatment	Early termination procedures
	Days							
	-28 to -2	-1	1	2-7	8, 9	10	14	
Urine pregnancy test (females)	X	X					X	X
FSH (post-menopausal females)	X							
Physical examination ³	X	X				X	X	X
Clinical laboratory tests (clinical chemistry, hematology, coagulation, and urinalysis)	X	X	X ¹	X ⁴	X	X	X	X
Vital signs	X	X	X ⁵	X	X	X	X	X
12-lead ECG ⁶	X ⁶	X ⁷	X ⁸	X ⁸	X	X	X	X
Telemetry			X ⁹	X ⁹				
PK blood sampling ¹⁰			X	X	X	X		
PK urine collection ¹¹			X	X	X	X		
Biomarker blood sampling			X ¹	X ²				
Blood sampling for possible future pharmacogenetic assessments		X ¹²						
Blood sampling for possible future metabolite assessments ¹⁰			X	X	X	X		
Blood sampling for possible future PD assessments			X ¹	X ²				
Prior/concomitant medications	X	X	X	X	X	X	X	X
AE monitoring ¹³	X	X	X	X	X	X	X	X

ACR = American College of Rheumatology; AE = adverse event; CDAI = clinical disease activity index; DAS28 = disease activity score 28; ECG = electrocardiogram; ESR = erythrocyte sedimentation rate; FSH = follicle stimulating hormone; HBc = hepatitis B core; HBsAG = hepatitis B surface antigen; HCV = hepatitis C virus; HIV = human immunodeficiency virus; ICF = informed consent form; IGRA-TB = interferon gamma release assay for tuberculosis; PD = pharmacodynamic; PK = pharmacokinetics; RT-PCR = reverse transcription polymerase chain reaction; SARS-CoV-2 = severe acute respiratory syndrome coronavirus 2; SDAI = simplified disease activity index.

1. Disease activity data (ACR20/50/70, DAS28, CDAI, SDAI, and blood sampling for ESR), blood for clinical laboratory tests, blood for biomarker assessments, and blood for possible future PD assessments will be collected prior to dosing on Day 1. Blood sampling for ESR will be collected and assessed at local laboratory.
2. Disease activity data (ACR20/50/70, DAS28, CDAI, SDAI, and blood sampling for ESR), blood for biomarker assessments, and blood for possible future PD assessments will be collected prior to dosing on Day 7 only. Blood sampling for ESR will be collected and assessed at local laboratory.
3. A full physical examination will be performed at the Screening Visit, Day 14, and Early termination visit; a brief physical will be performed on Days -1 and 10.
4. Blood for clinical laboratory tests will be withdrawn once on Days 4 and 7.
5. Vital signs will be collected at pre-dose and 1, 2, 4, 8, and 12 hours after dosing on Day 1.
6. 12-lead ECG will be conducted before blood sampling.
7. 12-lead ECG will be repeated once for eligibility confirmation at Screening and Day -1.
8. 12-lead ECG will be recorded at baseline and at 1, 2, 4, and 8 hours after dosing on Days 1 and 7.
9. Starting 2 hours prior to dosing and until 12 hours after dosing on Days 1 and 7.
10. Blood for PK sample analysis to determine parent and its metabolite concentrations and for possible future metabolite assessments will be sampled at pre-dose and 0.25, 0.5, 1, 1.5, 2, 3, 4, 6, 8, 12, 16, and 24 hours (pre-dose of Day 2) after dosing on Day 1, pre-dose on Days 3, 4, 5, 6, and on 7 at pre-dose and 0.25, 0.5, 1, 1.5, 2, 3, 4, 6, 8, 12, 16, 24, 48, and 72 hours after dosing on Day 7 (the sampling time points may be adjusted based on the PK results obtained from the previous parts or cohorts). The last dose will be administered on Day 7.
11. Urine for PK sample analysis will be collected at 0 (pre-dose) to 6, 6 to 12, and 12 to 24 hours after dosing on Day 1, and from 0 (pre-dose) to 6, 6 to 12, 12 to 24, 24 to 48, and 48 to 72 hours after dosing on Day 7. Urine collection intervals may be adjusted based on the PK results obtained from the previous parts or cohorts, e.g., if plasma PK sampling times are adjusted, the urine sampling times will be updated.
12. Sample will be obtained only from patients that consent to pharmacogenomics sampling.
13. Any AEs occurring after the patient signs the ICF will be collected and monitored throughout the study via safety assessments, observation, and patient reporting.

2 Introduction

TCK-276 is a highly potent, orally active, and selective cyclin dependent kinase 4/6 (CDK4/6) inhibitor. The Sponsor is planning to develop TCK-276 as a novel synthetic disease modifying antirheumatic drug (DMARD) with an alternative mechanism of action for the treatment of rheumatoid arthritis (RA).

The term “study intervention” throughout the protocol, refers to TCK-276.

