7.1.1 Overall Study Stopping Criteria

The study will be stopped if any of the following occur and are thought to be at least possibly related to study intervention agreed upon by the SRC:

- Two patients develop the same Grade 3 AE (grading is based on the Common Terminology Criteria for Adverse Events [CTCAE] version 5.0).
- One patient develops \geq Grade 4 AE (CTCAE version 5.0).
- Death of a patient at any time.

If any of the following scenarios occur within a cohort with reasonable possibility of a causal relationship with study drug, dosing will be stopped, and further dosing will not be initiated.

- One or more patients experience increased alanine ALT or AST $> 3 \times$ ULN with total bilirubin (TBL) $> 2 \times$ ULN or increased AST $> 3 \times$ ULN accompanied by alkaline phosphatase (ALP) $> 1.5 \times$ ULN.
- One or more patients experience a decrease of absolute neutrophil count less than 1,000/mm³ or white blood cell (WBC) less than $2.5 \times 10^3/\mu\text{L}$ or platelet count less than 75,000/ μL .
- One or more patients have an increase of more than 60 ms in QTcF compared to the baseline QTcF (baseline QTcF = value obtained on Day 1 at pre-dose in the treatment period) or QTcF > 500 ms or other clinically significant conduction disturbance or arrhythmia. All ECGs for this determination must be performed under strict resting conditions.
- Two or more patients, who receive study intervention, have tachycardia defined as resting supine heart rate > 125 beats per minute (bpm) persisting for at least 10 minutes.
- Two or more patients, who receive study intervention, have symptomatic bradycardia defined as resting supine heart rate < 40 bpm accompanied with symptoms of bradycardia while awake persisting for at least 10 minutes.
- Two or more patients, who receive study intervention, develop hypertension defined as an increase in resting supine systolic blood pressure (BP) > 40 mmHg to above a reading of 180 mmHg and persisting for at least 10 minutes.

If the criteria were met, the SRC will carefully review the totality of data, considering moderate non-serious AEs at least possibly related to the study intervention administration in unblinded

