8.3.2 Vital Signs

Vital signs will be assessed at the time points detailed in the SoA ([Table 1-1](#)). The following vital signs will be measured:

- Blood pressure (systolic and diastolic [mmHg])
- Pulse (bpm)
- Body temperature (tympanic [ear] or non-contact infrared thermometers) (°C)
- Respiratory rate (breaths per minute)

Supine BP and pulse recordings will be made after the patient has been recumbent and at rest ≥ 5 minutes.

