8.3.4 Cardiac Telemetry

To allow a real-time assessment of cardiac safety at the study site, patients will be monitored by cardiac telemetry (for real-time assessment of cardiac rate and rhythm). Any clinically significant change noted on telemetry will be followed up with a 12-lead ECG. Further evaluation and treatment will be performed as deemed appropriate by the Investigators. Irrespective of the intervention, the ECG and continuous cardiac monitoring will be repeated hourly until the event resolves or the patient is deemed clinically stable by the Investigators.

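### Timed post-dose vital signs are specified only on Day 1; on Days 2-7 they are scheduled with no time relative to dose, so no post-dose blood pressure is assured after repeated dosing

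*Protocol*

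**What the plan says.** Footnote 5 to protocol Table 1-1 (Section 1.3) reads: "Vital signs will be collected at pre-dose and 1, 2, 4, 8, and 12 hours after dosing on Day 1". SAP Table 6-1 carries the same footnote. The table row is "Vital signs X X X ⁵ X X X X X". Its eight marks stand for Screening, Day -1, Day 1, Days 2-7, Days 8 and 9, Day 10, Day 14 and early termination, and only the Day 1 mark has a note. Protocol Section 8.3.2 refers back to the table ("Vital signs will be assessed at the time points detailed in the SoA") and adds no times.

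Other dose-related measurements are handled differently:

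- ECG (footnote 8): "12-lead ECG will be recorded at baseline and at 1, 2, 4, and 8 hours after dosing on Days 1 and 7".
- Telemetry (footnote 9): "Starting 2 hours prior to dosing and until 12 hours after dosing on Days 1 and 7". Section 8.3.4 describes its purpose as "for real-time assessment of cardiac rate and rhythm".
- Plasma PK (footnote 10): full profiles after the Day 1 and the Day 7 dose.

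The primary objective (Synopsis and Section 3) is the safety and tolerability of multiple oral doses. Supine blood pressure, pulse, temperature and respiratory rate are among its variables. Section 4.3 regards seven days of dosing as enough to reach steady state. One cohort-level criterion in Section 7.1.1 applies when two or more patients "develop hypertension defined as an increase in resting supine systolic blood pressure (BP) > 40 mmHg to above a reading of 180 mmHg", persisting for at least 10 minutes.

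SAP 4.13.4 summarises vital signs by time point. SAP 4.2.5 leaves unscheduled readings out of summary statistics and figures unless they serve as baseline.

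**The concern.** The only vital-sign profile tied to dosing describes the response to a single dose, while the study's question is about repeated dosing. The protocol itself treats Day 7 as the reference day: the exposure limit is framed on Day 7 AUCtau, and the accumulation ratios compare Day 7 with Day 1. Yet blood pressure is not timed to the dose on that day, and no reason is given for treating it differently from ECG and telemetry.

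Two things are at stake. First, a short-lived change in blood pressure, temperature or respiratory rate after a later dose might not be measured, so the escalation review would have no assured information on it. Second, the Day 7 entry in the vital-signs summary has no defined meaning relative to dose. Readers could not tell whether it shows trough, post-dose or a mixture.

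**Working it through.** The plan states no figure to reproduce, so the check is a count of nominal times followed by a search for any other passage that fixes a vital-sign time.

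**1. Post-dose times fixed in Table 1-1 and its footnotes**

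| Assessment | Day 1 | Day 7 |
|---|---|---|
| Vital signs | 5 (1, 2, 4, 8, 12 h) | 0 |
| 12-lead ECG | 4 (1, 2, 4, 8 h) | 4 (1, 2, 4, 8 h) |
| Telemetry | -2 to +12 h | -2 to +12 h |
| Plasma PK | full profile to 24 h | 14 post-dose samples to 72 h |

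The vital-signs count for Days 2-6 is also 0. In the Days 2-7 column, vital signs are the only measurement with no note on day or time in either the cell or the row label.

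**2. Search elsewhere.** Protocol Sections 8.3.2 (vital signs), 8.3.3 (ECG) and 8.3.4 (telemetry) and the SAP schedule add no timed blood pressure after Day 1. Days 8, 9 and 10 fall about 24, 48 and 72 h after the last dose. Readings on those days do not describe the hours after dosing.

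**3. How many patients this concerns.** Active: 4 cohorts x 6 = 24. Placebo: 4 x 2 = 8. If every daily reading is taken before the morning dose, then 0 readings on Days 2-7 are post-dose in the 24 active patients. If every reading is taken after the dose, all are post-dose, but at unspecified times. The documents allow either.

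**4. Effect on the Day 7 summary.** Suppose a post-dose change of size d is absent at trough, and m of the 6 active patients in a cohort are read post-dose. The cohort mean change then reflects (m/6) x d: nothing for m = 0, half of d for m = 3 and all of d for m = 6. The table would not show which applied. The study is multi-center, so site practice may differ. A further reading taken at a site's discretion counts as unscheduled, and SAP 4.2.5 keeps it out of the summary.

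**5. Does Day 7 differ from Day 1 in exposure?** The documents give no half-life, so this is an illustration only. With once-daily dosing, linear kinetics and a single exponential decline, let k = 2^(-24/t½). The Day 7 to Day 1 ratio of AUCtau is then (1 - k^7)/(1 - k):

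| Assumed t½ | k | Day 7 / Day 1 |
|---|---|---|
| 6 h | 0.0625 | 1.07 |
| 12 h | 0.25 | 1.33 |
| 24 h | 0.5 | 1.98 |
| 48 h | 0.707 | 3.11 |

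Day 7 exposure could be almost the same as Day 1 or about three times as high. The count in step 1 holds in either case.

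**The case against.** The strongest reply is that this is a defensible Phase 1 choice. Safety pharmacology, including cardiovascular and respiratory studies, showed no untoward effects (Section 2.2.1). The single-dose study, with 48 subjects at up to 185 mg, reported no drug-related safety signals (Section 2.2.2). Blood pressure is not an adverse event of special interest. Patients are confined until Day 10 with continuous adverse-event monitoring, and Section 7.1.2 allows assessment times to be adjusted for later cohorts. All of this is true and limits the severity. It does not assure a post-dose blood pressure reading on any of Days 2-7. Single-dose capsule data in healthy subjects also do not settle repeated tablet dosing in patients.

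A reader might draw four stronger conclusions that the documents do not support:

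- That vital signs are absent after Day 1. They are scheduled on each of Days 2-7 and later, and a Days 2-7 reading may happen to fall after the dose.
- That exposure is known to peak on Day 7. Listing accumulation ratios as endpoints means accumulation will be measured, not that it is material.
- That an effect would be missed in all 32 patients. Eight are planned for placebo, and missing the effect in the other 24 requires every daily reading to be pre-dose.
- That the hypertension criterion in Section 7.1.1 cannot work. It is not limited to scheduled readings, and its persistence condition already calls for repeat measurement.

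**Conclusion.** The point holds as a gap in measurement timing. After Day 1, neither document ties a blood pressure, temperature or respiratory-rate reading to a post-dose time, although the primary objective concerns multiple doses. Heart rate and rhythm are covered on Day 7 by ECG and telemetry.

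The size is five fixed post-dose vital-sign times on Day 1 against none on Days 2-7, for 24 planned active patients. That count rests only on the text of the schedule. What would actually be lost depends on when sites take the daily reading, which the documents leave open, and on how much the drug accumulates, which they do not state.

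This is a worthwhile and cheap design improvement. It is not an internal contradiction, and no safety signal is shown to have been overlooked.

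**What to change.** - In protocol Table 1-1 and SAP Table 6-1, extend footnote 5 to cover Days 1 and 7. The minimum alternative is to add vital signs at the 1, 2, 4 and 8 h points already used for the Day 7 ECG.
- State one consistent time relative to dose for the Days 2-6 set. Which time is the sponsor's choice; what matters is that all sites use the same one.
- In SAP 4.13.4, tabulate Day 7 by nominal time, as for Day 1.

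The full Day 7 series would have six sets (pre-dose plus five). Counting the one already scheduled, that adds up to five readings. Patients are confined and already resting supine for the ECG at four of the five post-dose times, so no new visit is needed. The downside is a busier Day 7.

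Protocol Section 8.5.1 says that added time points for planned assessments are to be documented and approved but do not constitute an amendment. That text stands under the pharmacokinetics heading, so the sponsor should confirm that it applies to vital signs.
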